## 5.2 Trial Treatment(s)

The treatment(s) to be used in this trial are outlined below in [Table 2](#) and [Table 3](#).

In Arm 1, Part A, dose escalation will begin with 0.12 mg in cohorts of 2 subjects each, and will proceed based on safety events to a dose of 10 mg. Starting at a 30 mg dose (or at a lower dose as described in Section 5.2.1.3) in Part B, dose escalation will continue with a 3+3 design to identify a preliminary maximum tolerated dose (MTD). In Part C, dose confirmation will refine the estimate of the tolerability of the MTD (or maximum administered dose), using a toxicity probability interval [1].

Enrollment to Arm 2, (MK-1248 in combination with pembrolizumab) will begin once 2 subjects complete 1 cycle of MK-1248 monotherapy at the  $\geq 3$  mg dose level in Part A, and will follow a 3+3 design to identify a preliminary MTD in Part D. The starting dose of MK-1248 will be 0.12 mg. Doses of MK-1248 will be escalated as described in [Table 3](#) and the dose of pembrolizumab will be fixed at 200 mg. During 3+3 dose escalation, at least 2 days of observation will occur between each of the first 3 subjects at each dose level (except for the first 2 subjects receiving the combination treatment at the first dose level for which at least 7 days of observation between dosing will occur). Dose confirmation in Part E will refine the estimate of tolerability of the MTD using a toxicity probability interval [1].

Enrollment to both arms will occur in parallel with treatment allocation accomplished by non-random assignment to Arm 1 or Arm 2 using an IVRS/IWRS.

If pharmacodynamic saturation at the tissue level and/or robust clinical efficacy is observed during the dose escalation phase in either the monotherapy or combination therapy arm, initiation of the dose confirmation Parts C and E may begin. Depending on safety, efficacy and pharmacologic data, dose escalation in the monotherapy and combination therapy arms may continue concurrent with enrollment in Parts C and E. Up to a total of 14 subjects may be enrolled at a lower dose level where robust clinical activity is observed concurrent with the dose escalation phase. In either of the above cases, an administrative letter will be used to document the initiation of a dose confirmation cohort (Part C or E for the monotherapy or combination treatment, respectively), or to allow enrollment of up to a total of 14 subjects at a given dose.

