### 5.2.1.3 Accelerated Dose Escalation (MK-1248 Monotherapy)

During the accelerated dose escalation stage (Part A), each cohort will enroll two subjects and dose escalation will proceed as designated in [Table 2](#) and [Table 3](#), until a DLT is observed or until the dose level of 10 mg is safely administered. At least 2 days of observation will occur between each of the first 2 subjects at each dose level.

If a DLT is observed during a 2-subject cohort, an additional subject will be enrolled at this dose level for a total of 3 subjects, and the rules of 3+3 dose escalation described in Section 5.2.1.4 will apply:

- If the new subject does not develop a DLT (for a total of 1/3 subjects with a DLT at that dose level), three more subjects will be enrolled at this dose level and the rules of 3+3 design (Section 5.2.1.4) will be followed for a cohort of 6 subjects. The 3+3 dose escalation design will be followed from then on with 40% increments in the dose level.
- If the new subject develops a DLT (for a total of 2/3 subjects with a DLT at this dose level), the dose escalation stage of the trial will be terminated. The third subject will be enrolled in the dose directly below the current dose and the 3+3 dose escalation design will be followed from then on with 40% increments in the dose level.

See Section 5.2.2 for definition of DLTs.

Starting with the 30 mg dose, 3 subjects will be enrolled to each dose level.

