#### 5.2.1.4 3+3 Dose Escalation (MK-1248 Monotherapy and MK-1248 plus Pembrolizumab Combination)

During MK-1248 monotherapy (Arm 1), once the 10 mg dose is safely administered, starting with the next dose the study will proceed to 3 subjects enrolled at each dose level and dose escalation continuing according to [Table 2](#). During 3+3 dose escalation, at least 2 days of observation will occur between each of the first 3 subjects at each dose level.

For MK-1248, intermediate lower dose levels, not specified in [Table 2](#) and [Table 3](#) may be investigated. This escalation schedule may be adjusted downward based on PD, PK, and safety data emerging throughout the Phase 1 study.

The rules for the preliminary MK-1248 dose finding during MK-1248 monotherapy (Arm 1) and during MK-1248 plus pembrolizumab combination treatment (Arm 2) using the 3+3 design are as follows (all dose adjustments are made only to MK-1248):

An initial cohort of 3 subjects is enrolled.

- If 0/3 subjects develops a DLT, escalation to the next dose of MK-1248 will occur.
- If 1/3 subjects develops a DLT, another 3 subjects will be enrolled at this dose level.
  - If 0 of the 3 new subjects develops a DLT (for a total of 1/6 subjects with a DLT at this dose level), escalation to the next dose level will occur.
  - If  $\geq 1$  of the 3 new subjects develop a DLT (for a total of  $\geq 2/6$  subjects with a DLT at this dose level), the dose escalation stage of the trial will be terminated. If the dose directly below the current dose had been studied in at least 3 subjects, the dose directly below the current dose will be considered the preliminary MTD, and the study will proceed to the confirmation stage. If the dose directly below the current dose had been studied in  $< 3$  subjects, more subjects to a total of 3 will be enrolled at the dose directly below the current dose before proceeding to the confirmation stage.
- If  $\geq 2/3$  subjects develop a DLT, the dose escalation stage of the trial will be terminated. If the dose directly below the current dose had been studied in at least 3 subjects, the dose directly below the current dose will be considered the preliminary MTD, and the study will proceed to the confirmation stage. If the dose directly below the current dose had been studied in  $< 3$  subjects, more subjects to a total of 3 will be enrolled at the dose directly below the current dose before proceeding to the confirmation stage.

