#### **5.2.1.5 Dose Confirmation**

The objective of dose confirmation in Part C and Part E is to refine the estimate of the MK-1248 MTD based on TPI design [1] with target toxicity rate  $\leq 30\%$ . Dose confirmation involves the expansion of at least 1 dose level studied in the dose escalation stage of the study.

The toxicity probability interval (TPI) design [1] will be used at the dose confirmation stage. Based on the observed DLTs, the approach recommends actions of escalating, staying at, or de-escalating the dose level as presented in [Table 4](#).

Dose confirmation will begin with expansion of the preliminary MTD/MAD identified in the dose escalation stage described above. The dose confirmation part will continue until 14 subjects are studied at the selected dose (combined from dose escalation and dose confirmation) with  $\leq 5$  of 14 subjects experiencing a DLT. As subjects become evaluable for DLT assessment, the number of subjects who are evaluable for DLT versus the number of subjects who developed a DLT will be continuously assessed and de-escalation and re-escalation to eligible doses of MK-1248 will occur as shown in [Table 4](#)

The 200 mg dose of pembrolizumab will not be adjusted.

Table 4 Dose Confirmation Rules

Number of toxicities	Number of subjects treated at current dose										
	4	5	6	7	8	9	10	11	12	13	14
0	S	E	E	E	E	E	E	E	E	E	E
1	S	S	S	S	S	S	E	E	E	E	E
2	D	S	S	S	S	S	S	S	S	S	S
3	DU	D	D	S	S	S	S	S	S	S	S
4	DU	DU	DU	D	D	D	S	S	S	S	S
5		DU	DU	DU	DU	DU	D	D	S	S	S
6			DU	DU	DU	DU	DU	DU	D	D	D
7				DU	D						
8					DU						
9						DU	DU	DU	DU	DU	DU
10							DU	DU	DU	DU	DU
11								DU	DU	DU	DU
12									DU	DU	DU
13										DU	DU
14											DU

E = Escalate to the next higher dose  
 S = Stay at the current dose  
 D = De-escalate to the next lower dose  
 DU = The current dose is unacceptably toxic  
 Target toxicity rate = 30%  
 a=1; b=1; k1=1; k2=1.5; pow=1 per [1].

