### 8.4.3 Derivations of Efficacy/Immunogenicity/Pharmacokinetics Endpoints

Exploratory efficacy endpoints and their definitions are presented below.

**Objective Response Rate (ORR):** is defined as the percentage of subjects who have achieved confirmed complete response (CR) or partial response (PR) according to irRECIST by the investigator review. Subjects with missing outcome on objective response will be considered non-responders.

**Disease Control Rate (DCR):** is defined as the percentage of subjects who have achieved stable disease for at least 8 weeks or confirmed complete response (CR) or confirmed partial response (PR) according to irRECIST by the investigator review. Subjects with missing response will be considered not to have achieved DCR.

**Duration of Response (DOR):** is defined as the time interval between the date of the first confirmed response (CR/PR) (the response prior to confirmation) and the date of first documented disease progression based upon irRECIST by the investigator review. Response duration will be only determined for confirmed responses.

**Best Overall Response** per irRECIST [Appendix 12.6]: the best response attained during the study with 4 categories based upon irRECIST by the investigator review: Complete Response (CR), Partial Response (PR), Stable Disease (SD), and Progressive Disease (PD). Categories of CR and PR need to be confirmed in this endpoint.

**Progression-free Survival (PFS)**: is defined as the time from the start of treatment to progressive disease (PD) or death, whichever occurs earlier, based upon irRECIST by the investigator review. Subjects without documented PD/death will be censored at the last disease assessment date.

**Best Target Lesion Response** - maximum percent reduction in tumor line length over target lesions by the investigator review.

**Time to Confirmed Response** - defined only for subjects with confirmed response by the investigator review - the time interval between the start of treatment allocation and the date of the first confirmed response (CR/PR) (the response prior to confirmation).

Additional supportive analyses of these endpoints based on RECIST criteria and, if needed, central review might be conducted.

**PK endpoints**- serum concentrations of MK-1248 and pembrolizumab and derived PK parameters.

**Target engagement endpoints** – to be used in descriptive analyses

**Biomarker endpoints**– to be used in descriptive analyses

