## **8.6 Statistical Methods**

### **8.6.1 Statistical Methods for Efficacy Analyses**

This section describes the statistical methods that address the exploratory efficacy objectives.

For the subset of FAS1 subjects treated with the RP2D dose of MK-1248 and the subset of FAS2 subjects treated with the RP2D for combination of MK-1248 with pembrolizumab, the estimates of the ORR and DCR and the 95% confidence intervals for the estimates based on the Clopper-Pearson method [48] will be provided. For PFS, DOR, and time to confirmed response Kaplan-Meier plots will be provided. Graphic displays will be provided for the best target lesion response DOR.

The ORR, DCR, BOR, DOR, PFS, best target lesion response, and time to confirmed response in subjects treated with doses below the RP2 doses will be listed along with baseline characteristics.

For PFS, subjects without documented PD/death will be censored at the last disease assessment date or, if they started new anti-cancer treatment, at the last disease assessment before initiation of the new anticancer treatment.

Descriptive statistics will be provided for other exploratory efficacy parameters.

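### If the RP2D was expanded because activity was seen there, the planned pooled ORR and DCR keep the triggering subjects and are biased upward

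*Combined protocol and SAP*

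**What the plan says.** Section 5.2 gives two routes by which efficacy seen during escalation can add subjects to a dose. Parts C and E may start early: "If pharmacodynamic saturation at the tissue level and/or robust clinical efficacy is observed during the dose escalation phase". Separately, "Up to a total of 14 subjects may be enrolled at a lower dose level where robust clinical activity is observed" while escalation continues. In both cases a letter marks the decision; for the first route, "an administrative letter will be used to document the initiation of a dose confirmation cohort". Neither route has a numerical threshold.

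Subjects already treated at the dose count towards the target. The first route leads into dose confirmation, which under Section 5.2.1.5 runs until "14 subjects are studied at the selected dose (combined from dose escalation and dose confirmation"); the second speaks of a total of 14.

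Section 8.5.2 puts every dosed subject with measurable disease at baseline into FAS1 or FAS2. For the RP2D subset of each set, Section 8.6.1 plans "the estimates of the ORR and DCR and the 95% confidence intervals for the estimates based on the Clopper-Pearson method". Results at doses below the RP2D are listed with baseline characteristics. ORR "is defined as the percentage of subjects who have achieved confirmed complete response (CR) or partial response (PR") by irRECIST on investigator review. Sections 8.7 and 8.8 plan no interim analysis and no multiplicity control, and no text separates subjects treated before an expansion decision from those treated after it.

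**The concern.** If a dose is enlarged because responses were seen among its first few subjects, those subjects bring at least the triggering number of responders into the final count. Given that expansion took place, the total is no longer binomial at the true response rate. The pooled proportion is too high on average, and an interval that assumes a binomial count may not keep its stated error.

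Antitumor activity is exploratory objective 1, and the RP2D is the only dose in each arm for which the plan gives a response estimate with an interval. That figure is the one most likely to be carried into decisions about further development. The error favours the drug and, for a given trigger, grows as true activity falls.

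**Working it through.** **The plan's own figure.** Scenario 1 in Section 8.9.1 gives (8 + 27 + 11) + (39 + 11) = 46 + 50 = 96, as stated. It confirms that the RP2D group is a 3-subject escalation cohort plus 11, that is 14. The documents state no response rate or threshold to reproduce.

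**Inputs from the documents.** Total N = 14 at the dose. Subjects before expansion, n1: 3 in a 3+3 cohort, or 6, since "If 1/3 subjects develops a DLT, another 3 subjects will be enrolled at this dose level".

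**Assumptions.** True ORR p is 10% or 20%. The trigger is at least r confirmed responses among the first n1 subjects, with r = 1 or 2.

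**Formula.** With X1 responders among the first n1,

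E[ORR | expanded] = { E[X1 | X1 ≥ r] + (14 − n1)·p } / 14.

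**At p = 10%:**

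- n1 = 3, r = 1: P(trigger) = 1 − 0.9³ = 0.271; E[X1 | trigger] = 0.3/0.271 = 1.107; (1.107 + 1.1)/14 = 15.8%.
- n1 = 3, r = 2: P = 0.027 + 0.001 = 0.028; E = (2 × 0.027 + 3 × 0.001)/0.028 = 2.036; (2.036 + 1.1)/14 = 22.4%.
- n1 = 6, r = 1: P = 1 − 0.9⁶ = 0.469; E = 0.6/0.469 = 1.280; (1.280 + 0.8)/14 = 14.9%.
- n1 = 6, r = 2: P = 0.114; E = (0.6 − 0.354)/0.114 = 2.150; (2.150 + 0.8)/14 = 21.1%.

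**Bias and lower-limit error.** With 14 subjects the Clopper-Pearson lower limit exceeds 10% when there are 5 or more responders (limit 8.4% at 4, 12.8% at 5). Without any selection that has probability 0.9% at p = 10%. Given expansion:

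| n1, trigger | P(trigger), p = 10% | Bias, p = 10% | P(lower limit > 10%), p = 10% | Bias, p = 20% |
|---|---|---|---|---|
| 3, at least 1 | 27.1% | +5.8 | 2.7% | +4.5 |
| 3, at least 2 | 2.8% | +12.4 | 9.7% | +10.5 |
| 6, at least 1 | 46.9% | +4.9 | 1.9% | +3.0 |
| 6, at least 2 | 11.4% | +11.1 | 6.3% | +8.1 |

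Bias is in percentage points. Simulation with 1,000,000 draws per case gave the same expected rates at p = 10%.

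**Sensitivity at p = 10%.** In Part A "each cohort will enroll two subjects and dose escalation will proceed"; with n1 = 2 the bias is +6.1 (at least 1) or +12.9 (2 of 2). If enrollment stops at 10 subjects at the dose, the four tabulated triggers give +6.8 to +17.4.

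**Post-decision subjects only.** Their responses are independent of the trigger, so the expected ORR is p. Simulation gave 10.0% in all four cases. The sample falls to 14 − 3 = 11 or 14 − 6 = 8.

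**DCR.** A confirmed response also counts as disease control, so a response trigger pushes DCR upward too. The size depends on the true DCR, for which the documents give no basis, and is not computed here.

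**The case against.** Five points deserve an answer.

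- **Scope.** A reader might infer that every dose filled to 14 for activity yields a biased planned ORR. The documents do not support that: Section 8.6.1 estimates only at the RP2D, and a lower dose that does not become the RP2D is listed. The default confirmation dose is the DLT-driven preliminary MTD or MAD, which does not depend on response. This limits the point but does not remove it. Section 8.9.1 treats Parts C and E as the RP2D cohorts, and Section 5.2 lets those parts open on efficacy.
- **Trigger.** Robust activity is not defined as confirmed response. Tissue-level saturation can open Parts C and E, and unconfirmed shrinkage or prolonged stable disease might count as activity without guaranteeing a confirmed responder. This stands: the sizes above belong to the assumed triggers.
- **Interval.** A reader might infer that the interval loses its meaning whenever expansion follows activity. For one-response triggers at a true 10% the lower-limit error is 1.9% to 2.7%, close to or below 2.5%. There the damage is to the point estimate. The interval clearly fails only for the two-response triggers, which a single cohort meets with probability 2.8% or 11.4%.
- **Status.** Efficacy is exploratory, enrollment closed on 31 March 2017, and nothing in the documents shows that an activity-driven expansion occurred. A claim that the trial's reported ORR is in fact inflated would go too far.
- **Efficiency.** Dropping the earlier subjects costs precision. Mean squared error given expansion, pooled against post-decision only, is 0.0075 against 0.0113 (p = 10%, at least 1 of 6) and 0.0149 against 0.0200 (p = 20%, at least 2 of 6), so pooling wins there. It loses at p = 10% for at least 2 of 3 (0.0206 against 0.0082) and at least 2 of 6 (0.0167 against 0.0113). This stands, and argues for showing both figures rather than replacing one.

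**Conclusion.** The point holds conditionally. It applies when the dose that becomes the RP2D was expanded, or its Part C or E cohort opened, because of observed clinical activity. The pooled ORR and DCR in Section 8.6.1 then carry an upward selection bias that the plan neither separates nor labels. For ORR, under the assumed triggers and 14 subjects, it is about +5 to +12 points at a true 10% and +3 to +10.5 points at 20%. It would be larger if early closure left fewer subjects at the dose. Lower-limit error is materially above nominal only for two-response triggers. Because the endpoint is exploratory and the condition may not have arisen, this is a cheap reporting improvement and not a flaw in the trial's primary safety objectives.

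**What to change.** Add to Section 8.6.1: for an RP2D that was expanded, or whose Part C or E cohort was opened, because of observed clinical activity, ORR and DCR with Clopper-Pearson intervals are also reported for subjects allocated after the date of the administrative letter. They appear next to the pooled figure, which is labelled as including the triggering subjects and subject to selection.

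The letter is already required, so the cut-off date exists. The cost is one sentence and one extra table row with a wider interval, on 8 to 11 subjects at full enrollment and fewer given the early closure. If no such expansion took place, the sentence has no effect. One limit should be noted: the post-decision row removes the bias from the expansion decision only. If the RP2D was later chosen using those subjects' responses as well, that row is also subject to selection and should say so.

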## 5.2.1 Dose Selection/Modification

### 5.2.1.1 Dose Selection (Preparation)

The rationale for selection of doses to be used in this trial is provided in Section 4.0 – Background & Rationale.

Details on preparation of administration of MK-1248 and pembrolizumab are provided in the Procedure Manual.

### 5.2.1.2 Dose Escalation

In Arm 1 (MK-1248 monotherapy), dose escalation will begin with 0.12 mg in cohorts of 2 subjects each, and will proceed based on safety events to a dose of 10 mg. Starting at a 30 mg dose (or at a lower dose as described in Section 5.2.1.3) in Part B, dose escalation will continue with a 3+3 design to identify a preliminary maximum tolerated dose (MTD). In Part C, dose confirmation will refine the estimate of the tolerability of the MTD (or maximum administered dose), using a toxicity probability interval [1].

Enrollment to Arm 2, (MK-1248 in combination with pembrolizumab) will begin once 2 subjects complete 1 cycle of MK-1248 monotherapy at the  $\geq 3$  mg dose level in Part A, and will follow a 3+3 design to identify a preliminary MTD in Part D. The starting dose of MK-1248 will be 0.12 mg. Doses of MK-1248 will be escalated as described in [Table 3](#) and the dose of pembrolizumab will be fixed at 200 mg. Dose confirmation in Part E will refine the estimate of tolerability of the MTD using a toxicity probability interval [1].

### 5.2.1.3 Accelerated Dose Escalation (MK-1248 Monotherapy)

During the accelerated dose escalation stage (Part A), each cohort will enroll two subjects and dose escalation will proceed as designated in [Table 2](#) and [Table 3](#), until a DLT is observed or until the dose level of 10 mg is safely administered. At least 2 days of observation will occur between each of the first 2 subjects at each dose level.

If a DLT is observed during a 2-subject cohort, an additional subject will be enrolled at this dose level for a total of 3 subjects, and the rules of 3+3 dose escalation described in Section 5.2.1.4 will apply:

- If the new subject does not develop a DLT (for a total of 1/3 subjects with a DLT at that dose level), three more subjects will be enrolled at this dose level and the rules of 3+3 design (Section 5.2.1.4) will be followed for a cohort of 6 subjects. The 3+3 dose escalation design will be followed from then on with 40% increments in the dose level.
- If the new subject develops a DLT (for a total of 2/3 subjects with a DLT at this dose level), the dose escalation stage of the trial will be terminated. The third subject will be enrolled in the dose directly below the current dose and the 3+3 dose escalation design will be followed from then on with 40% increments in the dose level.

See Section 5.2.2 for definition of DLTs.

Starting with the 30 mg dose, 3 subjects will be enrolled to each dose level.

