## 2.0 TRIAL DESIGN

### 2.1 Trial Design

This is a non-randomized, multi-site, 2-arm, open-label trial of MK-1248 monotherapy (Arm 1) and MK-1248 in combination with pembrolizumab (Arm 2) in subjects with a histologically or cytologically confirmed diagnosis of any type of solid tumor who have measurable disease.

This trial will use an adaptive design based on the pre-specified criteria of dose limiting toxicity (DLT). For Dose Escalation (Parts B and D) a 3+3 dose escalation design will be utilized (See Section 5.2.1.4). For Dose Confirmation (Parts C and E) the toxicity probability interval (TPI) design [1] will be utilized to refine the estimate of maximum tolerated dose (MTD).

In Arm 1, MK-1248 monotherapy, dose escalation will begin with 2-subject cohorts (Part A) starting at a MK-1248 dose of 0.12 mg and will proceed based on adverse events to a dose of 10.0 mg or until a DLT occurs. If a DLT occurs, an additional subject will be enrolled and the rules of 3+3 as described in Section 5.2.1.4 will apply. Starting at a 30.0 mg dose in Part B, the study will continue with a 3+3 design to identify a preliminary maximum tolerated dose (MTD). During 3+3 dose escalation in both arms, an initial cohort of 3 subjects will be enrolled to a dose level. If none of the 3 subjects experiences a DLT, escalation to the next dose will occur. If one of the 3 subjects experiences a DLT, another 3 subjects will be enrolled at this dose level. If 1 DLT is observed among the 6 subjects, the dose escalation will continue. If  $\geq 2/3$  or  $\geq 2/6$  subjects at a dose level develop DLTs, dose escalation will be terminated, and the study will proceed to the dose confirmation stage at the previous dose level. At least 2 days of observation will occur between each of the first 3 subjects at each dose level (for Part A this applies to the 2 subjects enrolled). In Part C, dose confirmation will refine the estimate of the tolerability of the MTD (or maximum administered dose), using a toxicity probability interval.

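### Part A's third-subject rule has no exception for two DLTs in two subjects, although a third dosing could not then change the decision (minor fix)

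*Combined protocol and SAP*

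**What the plan says.** Part A of Arm 1 runs four dose levels (0.12, 0.6, 3 and 10 mg, Table 2) with two subjects each. The trigger for a third subject appears twice:

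- Section 5.2.1.3: "If a DLT is observed during a 2-subject cohort, an additional subject will be enrolled at this dose level for a total of 3 subjects".
- Section 2.1: "If a DLT occurs, an additional subject will be enrolled and the rules of 3+3 as described in Section 5.2.1.4 will apply".

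The same sections describe how long Part A runs. In 2.1 it "will proceed based on adverse events to a dose of 10.0 mg or until a DLT occurs", and in 5.2.1.3 it runs "until a DLT is observed or until the dose level of 10 mg is safely administered".

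Section 5.2.1.3 then lists two outcomes. The first opens "If the new subject does not develop a DLT (for a total of 1/3 subjects with a DLT at that dose level" and expands the level to six subjects. The second is a DLT in the new subject, counted as 2/3. It ends the dose escalation stage, and yet it goes on: "The third subject will be enrolled in the dose directly below the current dose", with 3+3 continuing from there in 40% steps.

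For two or more DLTs in three subjects, Section 5.2.1.4 says "subjects develop a DLT, the dose escalation stage of the trial will be terminated". The dose below is filled to three subjects if needed, and the study moves to confirmation. Section 2.1 also goes to confirmation. As an option, 5.2.1.4 allows an intermediate dose to be tested first.

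On spacing, 5.2.1.3 says "At least 2 days of observation will occur between each of the first 2 subjects at each dose level". The DLT window is the 21 days of Cycle 1 (Section 5.2.2).

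**The concern.** The trigger is a DLT, in the singular and without a count. In the two statements of how long Part A runs, the same phrase can only mean at least one. Read consistently, the trigger therefore covers a cohort in which both subjects had a DLT, and it enrols a third at that dose. The two listed outcomes show that the authors were thinking of exactly one DLT, because 1/3 and 2/3 are the totals reached from one.

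At stake is one subject dosed at a level that already meets the stopping boundary, in a first-in-human trial of an agonist antibody, with nothing gained for the escalation decision.

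A smaller problem follows. After a ≥2/3 outcome in Part A, the second outcome in 5.2.1.3 and the general rule in 2.1 and 5.2.1.4 lead to different next steps, and the protocol does not say which governs.

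**Working it through.** **The plan's own figure.** Section 8.9.1, Scenario 1 (no DLTs): Part A 4 × 2 = 8, Part B 9 × 3 = 27, Part C 14 − 3 = 11, so Arm 1 has 46. Part D 13 × 3 = 39 and Part E 14 − 3 = 11, so Arm 2 has 50. The total of 96 is reproduced. Because it assumes no DLTs, a change to the 2/2 case leaves it as it is. The plan gives no figure for the 2/2 case.

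**What the third subject can decide** (boundary ≥2/3, Section 5.2.1.4):

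| DLTs in first two | Third has no DLT | Third has a DLT |
|---|---|---|
| 1 | 1/3, expand | 2/3, stop |
| 2 | 2/3, stop | 3/3, stop |

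From 1/2 the third result decides. From 2/2 it does not. As an illustration, take the uniform prior that Section 8.9.2 uses for the DLT rate at the RP2D. After 2/2 the posterior is Beta(3,1), with mean 3/4 = 0.75 and P(rate > 30%) = 1 − 0.3³ = 0.973.

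**How often 2/2 would occur.** The documents give no DLT rate for MK-1248. I assume a rate p that is equal across the four doses, at 5% and 10%. Higher rates are not used, because Section 4.2.2.1 reports no DLTs for the related antibody up to 10 mg. A dose is reached in Part A's accelerated scheme only after 0/2 at every lower dose, so

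P(2/2 in Part A) = p² × [1 + (1−p)² + (1−p)⁴ + (1−p)⁶]

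- p = 0.05: 0.0025 × 3.452 = 0.0086
- p = 0.10: 0.0100 × 2.998 = 0.0300

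At 0.12 mg alone the chance is p² = 0.0025 or 0.0100.

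**How often both DLTs would be known in time.** Section 5.2.1.3 does not say whether the third subject waits for the second subject's window. I assume:

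- subject 1 is dosed on day 0 and subject 2 on day 2;
- DLT onset is uniform over 21 days;
- subject 3 is dosed L days after the first DLT and not before day 4.

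With onsets U₁ and U₂, both DLTs are known when −(L+2) ≤ U₂ − U₁ ≤ L − 2. Hence

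share = 1 − ½[(19−L)/21]² − ½[(23−L)/21]²

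with any negative bracket set to zero. For L = 2 this gives 0.1723, and the day-4 floor adds ½(2/21)² = 0.0045. The last two columns are the share times 0.0086 or 0.0300 (unrounded).

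| L (days) | Share known | Needless dosing, p = 5% | p = 10% |
|---|---|---|---|
| 2 | 0.177 | 0.15% | 0.53% |
| 7 | 0.546 | 0.47% | 1.64% |
| 14 | 0.880 | 0.76% | 2.64% |
| 23 | 1.00 | 0.86% | 3.00% |

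Both windows close by day 2 + 21 = 23, inside the 4 weeks per Part A dose assumed in Section 8.9.1.

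**Follow-on after a Part A stop.** The second outcome in 5.2.1.3 goes back one level and climbs in 40% steps. The general rule goes to confirmation at the level below. The levels that lie between are:

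- 0.12 to 0.6 mg: 0.168, 0.235, 0.329, 0.461 (four)
- 0.6 to 3 mg: 0.84, 1.18, 1.65, 2.30 (four)
- 3 to 10 mg: 4.2, 5.88, 8.23 (three)

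So the choice between the routes matters for which doses are tested.

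**The case against.** The best case for the plan is that 2/2 is an unaddressed case and not an instruction. The trigger resolves into two outcomes that are possible only after exactly one DLT, so it should be read together with them. That is a fair account of the intent. It still leaves 2/2 without a rule, and the trigger as worded includes it. Either reading calls for the same sentence.

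Other controls reduce the risk. Allocation is central and depends on whether an arm is open (Section 5.3). The sponsor and investigators follow individual data as they arrive and review safety before the next cohort (Section 7.1.2.1). A mechanical third dosing is therefore less likely. However, the third subject joins the same cohort, so the review before the next one does not clearly cover it.

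The ordinary 3+3 in 5.2.1.4 likewise has no explicit stop in mid-cohort, so Part A is not uniquely careless. This stands as a limit on severity. The difference is that in Part A the DLT itself triggers the extra dosing.

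When the second DLT is not yet known, dosing a third subject is the correct action at 1/2. The fix must respect this.

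Three stronger readings are tempting and are not supported:

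- A reader might infer that after 2/2 and a clean third subject the plan orders three more at that dose, because the first outcome is keyed to the new subject. That outcome is labelled 1/3, and the ≥2/3 rule stops escalation.
- A reader might infer that 5.2.1.3 and 5.2.1.4 flatly contradict each other. Section 5.2.1.4 allows an intermediate dose in place of going directly to confirmation. Its clause on fewer than three subjects at the dose below also has its own use, for a stop at 30 mg when 10 mg has had only two.
- A reader might infer that a stop at 0.12 mg has no way forward, since Table 2 has no lower dose. Section 5.2.1.4 permits lower intermediate doses that are not in the table.

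**Conclusion.** The concern holds as a minor, cheap safety improvement. The trigger in 5.2.1.3 and 2.1 covers 2/2, its listed outcomes do not, and a third dosing after two known DLTs cannot alter the stop.

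The size is at most one needless exposure, with a chance of about 0.15% to 3%. That range rests on assumed DLT rates of 5% to 10%, equal across the Part A doses, on uniform DLT onset over 21 days, and on the assumed lag to the third dosing. The table of decisions needs none of these assumptions.

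The secondary point is a matter of wording: the plan should name which follow-on applies after a Part A stop. No estimate or analysis changes, and with enrolment closed on 31-Mar-2017 the correction serves the accuracy of the rule and any reuse of it. A reader might infer that someone in this trial was needlessly dosed. The documents report no 2/2 cohort and do not support that.

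**What to change.** 1. In 5.2.1.3 and 2.1, limit the third-subject rule to exactly one of two subjects with a DLT.
2. Add: if both DLTs are known before a third subject is dosed, no further subject is enrolled at that dose, and the cohort is handled as a ≥2/3 outcome.
3. In the second outcome of 5.2.1.3, say that the accelerated dose escalation stage ends. State that this outcome, as the specific Part A rule, governs over the move to confirmation in 2.1 and 5.2.1.4. If the sponsor prefers the confirmation route, that outcome has to be rewritten. What matters is that one route is stated.

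The cost is a few sentences. No decision-relevant data are lost and the planned 96 subjects stand. The route in item 3 is already in the protocol. With no further DLTs it would use up to 4 × 3 = 12 subjects at intermediate levels after a stop at 0.6 or 3 mg, or 3 × 3 = 9 after a stop at 10 mg.
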